5.1.4. Muscle Discomfort

In clinical studies of hydroxychloroquine, patients may have increases in muscle discomfort above baseline upon initiation of treatment, please refer to the package insert for a detailed discussion.

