6.2.2. Secondary Efficacy Endpoints

Time-to-first clinical event consisting of a persistent change for any of the following:

- One positive NP sample
- Common clinical symptoms of COVID-19 infection including fever, cough, and shortness of breath
- Less common signs and symptoms of COVID-19 infection including headache, muscle pain, abdominal pain, sputum production, and sore throat

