7. INVESTIGATIONAL PLAN

7.1. Overall Study Design

This prospective open label trial will study the safety, tolerability, and efficacy of hydroxychloroquine in qualified health care workers.

Qualified individuals will be administered hydroxychloroquine twice a day on day 1 (two 200 mg twice a day) and once a week (two 200 mg) afterwards for a total of 7 weeks. Dose de-escalation is permitted during the study if indicated clinically. Please refer to [Section 7.3.1](#) for additional details on dose de-escalation.

All study individuals will follow the same visit and assessment schedule. Following study enrollment, participants will be scheduled to be assessed in person at Days 7, 14, 21, 28, 35, 42 and 49.

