7.3. Treatment Assignment

Qualified individuals may choose which group they want to be in. Subjects in the treatment group will receive hydroxychloroquine for 7 weeks. Those who decide to opt out of receiving treatments will compose the control group.

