9.1.5. Management of COVID-19 positive test

If the result of an NP swab test demonstrates the presence of SARS-CoV-2, the subject will be directed to immediately receive appropriate medical care and will discontinue study treatment and procedures, however the sponsor will continue to follow the subject until their condition is resolved or death. Patient management following a positive test during the study will not be directed by study procedures and will be at the discretion of the subject's physician.

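### The open-label secondary composite counts unconfirmed symptoms, one of them overlapping with a named drug effect, and its persistence rule is undefined

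*Protocol*

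**What the plan says.** Protocol 6.2.2, repeated in the synopsis and in SAP 4.2, gives the secondary efficacy endpoint as "Time-to-first clinical event consisting of a persistent change for any of the following". Three items follow, and any one is enough:

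- a swab result, worded as "One positive NP sample";
- a first symptom group, worded as "Common clinical symptoms of COVID-19 infection including fever, cough, and shortness of breath";
- a second symptom group, worded as "Less common signs and symptoms of COVID-19 infection including headache, muscle pain, abdominal pain, sputum production, and sore throat".

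Neither document links a symptom to a positive swab or provides for adjudication. Neither says how long, or over how many visits, a change must last to be persistent, or which date then counts as the event.

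On design, Protocol 7.1 states: "This prospective open label trial will study the safety, tolerability, and efficacy of hydroxychloroquine in qualified health care workers". Protocol 7.3 adds: "Qualified individuals may choose which group they want to be in". Those who decline the drug become the controls and take no placebo.

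On the drug, Protocol 5.1.4 warns that "patients may have increases in muscle discomfort above baseline upon initiation of treatment", and 9.1.2 advises on managing it.

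On what follows a positive swab, Protocol 9.1.5 says the subject "will discontinue study treatment and procedures", although the sponsor keeps following the subject to resolution or death. Protocol 8.4.1 lists a positive test among the reasons for stopping study drug, then expects such subjects to complete the remaining visits and assessments where possible.

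The survival analysis in Protocol 12.2.1 and SAP 6.1 concerns COVID-19-free survival. No analysis of this composite is described.

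**The concern.** There are two separate faults.

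*What counts as an event.* A treated participant who develops muscle pain from the drug can be scored as an efficacy failure. A control cannot have that event. Headache or sore throat from any other cause also counts, in both groups, and makes the groups look more alike. Participants know and chose their treatment, so how readily they report a symptom may differ by group, in a direction nobody can state beforehand.

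*When the event occurs.* Read literally, the persistence requirement governs all three items, including the single swab. Even if it was meant for symptoms alone, it has no definition. Two programmers could derive different events and dates from the same data.

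At stake is whether a composite result, favourable or unfavourable, can be read as saying anything about prevention of COVID-19.

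**Working it through.** The plan states no event rate, power or sample size for this composite, so there is no figure to reproduce. The size below is an illustration.

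**Inputs from the documents**
- Protocol 12.1 and SAP 2.1 put infection at 30% in the clinical arm and 40% lower than in controls, so the control rate is 0.30/0.60 = 0.50.
- Reading 30% as the control rate instead gives 0.30 x 0.60 = 0.18 on drug. That reading yields the planned total: 156 per arm for 80% power, and 156 x 1.15 = 179.4, or 180 per arm. Both readings are therefore shown.
- Evaluable participants: 180 x 0.85 = 153 per arm. Test: one-sided 0.05.

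**Assumed inputs (no source in the documents)**
- b, persistent symptoms of other cause, equal in both groups: 20%.
- x, persistent drug-related symptoms, drug group only: 5-10%.
- Infection (p), b and x are independent.

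**Formulas**
- Control: 1 - (1-p)(1-b)
- Drug: 1 - (1-p)(1-b)(1-x)

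For example, on drug with p = 0.30, b = 0.20 and x = 0.05: 1 - 0.70 x 0.80 x 0.95 = 0.468. Power is for comparing the two proportions.

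| Infection, control vs drug | b | x | Composite, control | Composite, drug | Ratio | Power |
|---|---|---|---|---|---|---|
| 0.50 vs 0.30 | 0 | 0 | 0.500 | 0.300 | 0.60 | 97.5% |
| 0.50 vs 0.30 | 20% | 0 | 0.600 | 0.440 | 0.73 | 87.9% |
| 0.50 vs 0.30 | 20% | 5% | 0.600 | 0.468 | 0.78 | 75.0% |
| 0.50 vs 0.30 | 20% | 10% | 0.600 | 0.496 | 0.83 | 57.3% |
| 0.30 vs 0.18 | 0 | 0 | 0.300 | 0.180 | 0.60 | 79.4% |
| 0.30 vs 0.18 | 20% | 0 | 0.440 | 0.344 | 0.78 | 53.0% |
| 0.30 vs 0.18 | 20% | 5% | 0.440 | 0.377 | 0.86 | 30.1% |
| 0.30 vs 0.18 | 20% | 10% | 0.440 | 0.410 | 0.93 | 13.4% |

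**Wider range.** With b from 0 to 50% and x from 0 to 20%, the ratio runs from 0.60 to 0.96 on the first reading and from 0.60 to 1.15 on the second. The drug-only excess that hides the whole effect is 1 - 0.50/0.70 = 28.6% or 1 - 0.70/0.82 = 14.6%.

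**No true effect.** With infection at 30% in both groups and b = 20%, x of 5-10% gives 0.468-0.496 against 0.440, a ratio of 1.06-1.13.

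**Reporting alone.** Again with infection at 30% in both groups, let one group report other symptoms at 20% and the other at 30%: 0.44 against 1 - 0.70 x 0.70 = 0.51. The ratio is 1.16 if the drug group reports more and 0.86 if controls do. Either way the chance of a significant one-sided result in that direction is 33.7% rather than 5%.

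**Persistence, side by side.** Read literally, 6.2.2 needs something beyond one positive swab to show that positivity lasted. Under 9.1.5 no further study swab would be taken; under 8.4.1 it would. Whether the component can be observed depends on which section a site follows.

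**The case against.** Much of the case on the other side stands, and it limits the point.

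- A reader might infer that the composite overlaps with drug effects generally, including gastrointestinal ones. The documents do not show that. Diarrhea and nausea (9.1.3, 9.1.4) are not components, and abdominal pain is not named as a drug effect. The overlap is one of eight listed symptoms, and 5.1.4 says discomfort, not pain.
- A reader might infer that persistence of a positive swab can never be observed. That follows from 9.1.5 alone; 8.4.1 points the other way. The documents conflict, so it *may* not be observable.
- The stem can be read as applying persistence to symptoms only. The fault is then an undefined term rather than a contradiction. The date of a symptom event still cannot be derived.
- Persistence is presumably meant to screen out passing complaints. For that reason b and x above stand for persistent symptoms only, and they could be small.
- At b = 20%, more than half of the movement away from 0.60 comes from other-cause symptoms (to 0.73 or 0.78 before any drug effect is added). That is dilution, not bias against the drug.
- The synopsis promises that outcomes are captured and defined alike in both groups. This helps, but it does not remove knowledge of treatment. Symptoms are elicited by a non-directed question (11.3). Table 3 has no symptom checklist beyond temperature, the cough scale and adverse events, and adverse-event collection is tied to a first dose (11.2.1.1) that controls never take.

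The endpoint is secondary, with no alpha or power attached to it.

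**Conclusion.** The point holds in a limited form: the composite is open to bias and cannot be derived unambiguously as worded. A reader might go further and conclude that it is biased against hydroxychloroquine. The documents do not support that. Drug-related muscle pain pushes that way, other-cause symptoms pull towards no difference, and open-label reporting could push either way, so the net direction is unknown.

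The size rests wholly on the assumed symptom rates and on independence. It is a shift from a true ratio of 0.60 to 0.78-0.83 on the planned rates as written, or to 0.86-0.93 if 30% is the control rate. The PCR-based primary endpoint does not use symptoms and is untouched. The change is worth making because it is cheap and decides whether a composite result can be interpreted.

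**What to change.** 1. Define the swab component as the first positive NP sample. Apply persistence to symptoms only, stating the number of visits required and which date is the event date.
2. Report each component by group, with the less common symptoms shown separately and muscle pain on its own line. Record the listed symptoms in the same way in both groups at every weekly visit.
3. Add a companion endpoint of symptomatic PCR-confirmed infection: a listed symptom *and* a positive NP sample at that visit or the next weekly one. A version counting a positive swab *or* a swab-confirmed symptom would not serve, because every such participant already has a positive swab. It would have the same participants with events as the primary endpoint, with only some dates moved.
4. Reconcile Protocol 8.4.1 and 9.1.5 on what happens after a positive swab, and name the analysis of the composite in the SAP.

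Cost: endpoint and SAP wording, and a short symptom list on the visit form. The companion will have fewer events. It will also miss symptoms that begin only after the first positive swab if no later study swab is taken, which is a further reason to settle item 4.

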6.2.3. Exploratory Efficacy Endpoints

Time-to-first clinical worsening event consisting of any of the following:

- 1) Hospitalization for COVID-19 infection
- 2) Intensive care unit admission for COVID-19 infection
- 3) All cause death

6.2.4. Safety Endpoints

Frequency, intensity, and relationship to study drug of adverse events and serious adverse events, change from baseline in body temperature.

7. INVESTIGATIONAL PLAN

7.1. Overall Study Design

This prospective open label trial will study the safety, tolerability, and efficacy of hydroxychloroquine in qualified health care workers.

Qualified individuals will be administered hydroxychloroquine twice a day on day 1 (two 200 mg twice a day) and once a week (two 200 mg) afterwards for a total of 7 weeks. Dose de-escalation is permitted during the study if indicated clinically. Please refer to [Section 7.3.1](#) for additional details on dose de-escalation.

All study individuals will follow the same visit and assessment schedule. Following study enrollment, participants will be scheduled to be assessed in person at Days 7, 14, 21, 28, 35, 42 and 49.

7.2. Number of Subjects

A total of 360 subjects will be enrolled

7.3. Treatment Assignment

Qualified individuals may choose which group they want to be in. Subjects in the treatment group will receive hydroxychloroquine for 7 weeks. Those who decide to opt out of receiving treatments will compose the control group.

7.3.1. Dose and Dose De-Escalation

Subjects receiving hydroxychloroquine will start at fixed doses unless contraindicated clinically. The investigator may choose to decrease the subject's dose to one-half of the prior doses if clinically indicated. Dose de-escalation can occur more than once, but the minimum dose permitted is 200 mg of hydroxychloroquine. Reasons for dose de-escalation should be discussed with the medical monitor prior to changing dose.

Unscheduled visits due to dose de-escalation should include assessments detailed in [Section 9.5](#).

7.4. Criteria for Study Termination

Although the Sponsor intends to complete the study, the Sponsor reserves the right to discontinue the study at any time for clinical or administrative reasons, or if required by regulatory agencies. If the Sponsor discontinues the study, all study drug will be discontinued and the investigator will be responsible for securing any alternative therapy to be administered, as appropriate.

7.5. Schedule of Assessments

[Table 3](#) lists the overall schedule of assessments for the study.

Table 3: Schedule of Assessments

Assessment	Study Day (Day)	Screen A ^a	Day 1 ^b	Day 7 Day 7±3	Day 14 Day 14±3	Day 21 Day 21±3	Day 28 Day 28±3	Day 35 Day 35±3	Day 42 Day 42±3	Day 49 ^j Day 49±3 (End of study visit)
Informed consent		X								
Inclusion/ exclusion		X	X ^c							
Self-reported Pregnancy Status ^d		X	X	X	X	X	X	X	X	X
Demographics and baseline disease characteristics		X								
Prior and Concomitant medications		X	X	X	X	X	X	X	X	X
Current background medications		X	X	X	X	X	X	X	X	X
Medical history		X								
Self-reported Height		X								
Self-reported Weight		X								
Body temperature		X	X	X	X	X	X	X	X	X
Study drug administration			X	X	X	X	X	X	X	
Dispense study drug ^e			X	X	X	X	X	X	X	
Collect study drug ^f				X	X	X	X	X	X	X
nasopharyngeal (NP) sampling			X	X	X	X	X	X	X	X
Adverse event collection			X ^g	X	X	X	X	X	X	X
Visual analogue scale (VAS) for cough severity		X	X	X	X	X	X	X	X	X
Exposure assessment		X	X	X	X	X	X	X	X	X
Virus serology ^h		X			X		X		X ⁱ	

^a Total Screening period should not exceed 30 days. Screening and Day 1 can be completed in the same visit.

^b Day 1 is the day of administration of the first dose. **On Day 1, all procedures should be performed before study drug administration.**

^c Screening eligibility procedures do not need to be repeated on Day 1; however, a review of any changes in eligibility criteria should be evaluated prior to Day 1 procedures

^d Female participants will be asked with respect to their pregnancy as a verbal check

^e Depending on the availability of the drug supply, the schedule of drug dispensing might change

^f If the schedule for drug dispensing changes, the arrangements for drug collection will change accordingly

^g AE assessments on Day 1 should be performed following study drug administration

^h Only applicable to those who choose to participate in the optional viral serology study

ⁱ Individuals who terminate from the study prior to the Day 49 study visit should return to the clinic as soon as possible for early termination assessments (*i.e.*, Day 49 Day Prior and end-of-treatment visits). Participants should complete the end-of-treatment procedures, including assessments, prior to any adjustments being made to their treatment regimen.

^j If final serology draw not collected at Day 42, it can be collected at day 49

8. SELECTION AND WITHDRAWAL OF SUBJECTS

8.1. Subject Inclusion Criteria

1. Adult male and female healthcare workers ≥ 18 to ≤ 75 years of age upon study consent
 2. Healthcare workers with
 - One day or more of exposure to suspect and/or positive COVID-19 patients, including but not limited to those working in the Emergency Department or Intensive Care Unit.
- OR
- Unprotected exposure to a known positive COVID-19 patient within 72 hours of screening.
3. Afebrile with no constitutional symptoms
 4. Willing and able to comply with scheduled visits, treatment plan, and other study procedures
 5. Evidence of a personally signed and dated informed consent document indicating that the subject (or a legally acceptable representative) has been informed of all pertinent aspects of the study prior to initiation of any subject-mandated procedures

8.3. Subject Re-Screening

Subjects may repeat the Screening procedures to qualify for the study with approval from the medical monitor.

8.4. Subject Discontinuation and Termination

Subjects have the right to discontinue study drug or withdraw from the study at any time for any reason, without prejudice to their medical care. Furthermore, the investigator may discontinue a subject from study drug. Consultation with the medical monitor should occur prior to study drug discontinuation or withdrawing a subject from the study. The reason for a subject's discontinuation from study drug or study termination will be recorded in the electronic case report form (eCRF).

8.4.1. Subject Discontinuation Criteria

Discontinuation refers to a subject's stopping administration of study drug. Reasons for study drug discontinuation may include the following:

- Confirmed clinical worsening event
- Occurrence of an AE or change in medical status that leads the investigator to be concerned about the subject's welfare
- Administrative reasons (e.g., inability to continue)
- Sponsor termination of the study
- Voluntary withdrawal
- Females who become pregnant during the study
- A positive COVID-19 test

Subjects who are discontinued from study drug should still continue in the study, completing all study visits and undergo all scheduled study assessments, if possible.

8.4.2. Subject Termination Criteria

Termination refers to a subject's stopping study drug and all study assessments and visits. Reasons for study termination include the following:

- Loss to follow-up

- Death
- Withdrawal of consent

Every reasonable effort should be made to contact individuals who do not return for a scheduled visit. The investigator should inquire about the reason for withdrawal, request the subject return all unused investigational product, request the subject return for end-of-treatment and follow-up visits (if applicable), and follow up with the subject regarding any unresolved AEs.

9. TREATMENT OF SUBJECTS

9.1. Select Management Guidelines

The following guidelines apply to the management of study participants:

9.1.1. Management of Ongoing Exposures

Study participants will continue to adhere to good clinical practice to avoid infection with COVID-19 according to the CDC and other applicable guidance.

9.1.2. Management of Muscle Discomfort

Basic symptomatic relief is the first step in managing muscle spasm, including walking, adequate hydration, wearing socks, and stretching before bedtime. Assessment of levels of electrolytes such as magnesium, calcium and potassium may indicate the need for replacement. If vitamin D levels are low, supplementation may be warranted. Muscle relaxants may also help relieve symptoms.

9.1.3. Diarrhea

In instances where an individual experiences diarrhea consideration will be made with respect to the doses of the study medications as well as concomitant medications.

9.1.4. Nausea

Nausea may occur with higher doses of hydroxychloroquine.. Nausea adverse events are typically mild and reversible within a few Days after treatment initiation. If symptoms do not resolve, dose de-escalation, with consultation of the medical monitor, may be necessary.

9.1.5. Management of COVID-19 positive test

If the result of an NP swab test demonstrates the presence of SARS-CoV-2, the subject will be directed to immediately receive appropriate medical care and will discontinue study treatment and procedures, however the sponsor will continue to follow the subject until their condition is resolved or death. Patient management following a positive test during the study will not be directed by study procedures and will be at the discretion of the subject's physician.

9.2. Description of Study Drug

Hydroxychloroquine (BRI-001) drug product information is shown in [Table 4](#).

Table 4: Hydroxychloroquine Drug Product Information

Description	Hydroxychloroquine tablets
Ingredients	Hydroxychloroquine sulfate
Route of Administration	Oral

9.3. Concomitant Medications

9.3.1. Excluded Medications

Subjects taking these medications or treatments will be ineligible for enrollment:

- Any other investigational drug or device as part of an interventional study;
- Taking Digoxin, Mefloquine, methotrexate, cyclosporine, praziquantel, antacids and kaolin, cimetidine, ampicillin, Insulin or antidiabetic drugs, arrhythmogenic drugs, antiepileptic drugs, loop, thiazide, and related diuretics, laxatives and enemas, amphotericin B, high dose corticosteroids, and proton pump inhibitors, neostigmine, praziquantel, Pyridostigmine, tamoxifen citrate

Subjects who take excluded medications during the study should not discontinue study drug solely on this basis. Consultation with the medical monitor should occur prior to study drug discontinuation or withdrawing a subject from the study.

9.3.2. Permitted Medications

Allowed concomitant medications include the following:

- Daily multivitamins or recommended daily supplements;
- Other medications intended to manage concurrent diseases, as authorized by the treating physician;
- Oral, implantable, or injectable contraceptives.

Subjects taking medication chronically should be maintained on those same doses and dose schedules throughout the study period and should not have additions or changes made to their medications, as medically feasible.

The use of the other therapies which may affect walking distance, are permitted during the study, provided the subjects have been receiving a stable dosage for at least 30 days prior to Day 1. Unless medically indicated and discussed with the medical monitor, the doses of these agents should remain unchanged during the study.

9.4. Treatment Compliance

The investigator or his/her designated and qualified representatives will only dispense study drug to subjects enrolled in the study in accordance with the protocol. The study drug must not be used for reasons other than that described in the protocol. Subjects who miss more than 25% of the total number of expected doses will not be considered treatment-compliant.

9.4.1. Study Monitoring Committee

A study monitoring team including a qualified physician, a monitor from BSWRI, and a statistician will be responsible to monitor the safety and integrity of the study and to make recommendations as appropriate. They will start reviewing the collected data approximately 4

weeks after the first subject is enrolled and will continue to do so quarterly until the last dose of the last subject enrolled.

The study monitoring committee will be responsible for reviewing the progress of the study and the accumulating of the data while the study is ongoing. They may recommend that the study continue as is, be modified to protect subject safety, or be terminated. However, investigators, will make decisions concerning the need for laboratory investigations, ECG, and intra-subject dose-escalation decisions throughout the study for each subject and may choose to decrease the subject's dose (to one-half of the prior dose).

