2. SYNOPSIS

Name of Sponsor/Company: Baylor Scott and White Research Institute	
Name of Investigational Products: Hydroxychloroquine 200 mg tablets	
Title of Study: A PROSPECTIVE CLINICAL STUDY OF HYDROXYCHLOROQUINE IN THE PREVENTION OF SARS-COV-2 (COVID-19) INFECTION IN HEALTH CARE WORKERS AFTER HIGH-RISK EXPOSURES	
Study center(s): Single center	
Studied period: 4 months Estimated date first subject enrolled: March 2020 Estimated date last subject completed: July 2020	Phase of development: 2
Objectives: For Healthcare workers with 
 One day or more of exposure to suspected and/or positive COVID-19 patients, including but not limited to those working in the Emergency Department or Intensive Care Unit. OR Unprotected exposure to a known positive COVID-19 patient within 72 hours of screening. Primary: 
 To assess the efficacy of hydroxychloroquine 400 mg (two 200 mg tablets) twice a day on day 1 followed by two 200 mg tablets once a week for a total of 7 weeks in the prevention of COVID-19 infection Secondary: 
 To compare the rate of COVID-19 positive conversion among emergency department workers versus intensive care unit workers 	
Endpoints: Primary Efficacy Endpoint: Rate of COVID-19 positive conversion on weekly nasopharyngeal (NP) sampling Secondary Efficacy Endpoint: Time-to-first clinical event consisting of a persistent change for any of the following: 
 One positive NP sample Common clinical symptoms of COVID-19 infection including fever, cough, and shortness of breath Less common signs and symptoms of COVID-19 infection including headache, muscle pain, abdominal pain, sputum production, and sore throat Exploratory Efficacy Endpoint: Time-to-first clinical worsening event consisting of any of the following: 
 Hospitalization for COVID-19 infection Intensive care unit admission for COVID-19 infection All cause death 	

Safety:

Participants will be closely monitored for any occurrence of adverse events or serious adverse events during the trial. Weekly in-person visits will be scheduled to capture the frequency, intensity, and relationship to study drug of (serious) adverse events. Body temperature will also be collected in all follow-up visits.

Methodology:

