2. Unwilling to practice acceptable methods of birth control (both males who have partners of childbearing potential and females of childbearing potential) during Screening, while taking study drug, and for at least 30 days after the last dose of study drug is ingested

Note: the following criteria follow standard clinical practice for FDA approved indications of this medication

3. Having a prior history of blood disorders such as aplastic anemia, agranulocytosis, leukopenia, or thrombocytopenia
4. Having a prior history of glucose-6-phosphate dehydrogenase (G-6-PD) deficiency
5. Having dermatitis, psoriasis or porphyria
6. Taking Digoxin, Mefloquine, methotrexate, cyclosporine, praziquantel, antacids and kaolin, cimetidine, ampicillin, Insulin or antidiabetic drugs, arrhythmogenic drugs, antiepileptic drugs, loop, thiazide, and related diuretics, laxatives and enemas, amphotericin B, high dose corticosteroids, and proton pump inhibitors, neostigmine, praziquantel, Pyridostigmine, tamoxifen citrate
7. Allergies: 4-Aminoquinolines
8. Pre-existing retinopathy of the eye
9. Has a chronic liver disease or cirrhosis, including hepatitis B and/or untreated hepatitis
10. Untreated or uncontrolled active bacterial, fungal infection
11. Known or suspected active drug or alcohol abuse, per investigator judgment
12. Women who are pregnant or breastfeeding
13. Known hypersensitivity to any component of the study drug
14. A known history of prolonged QT syndrome or history of additional risk factors for torsades de pointe (e.g., heart failure, requires a lab test , family history of Long QT Syndrome), or the use of concomitant medications that prolong the QT/QTc interval

Investigational product, dosage and mode of administration:

Oral hydroxychloroquine 400 mg twice a day (two 200 mg tabs twice a day) on day 1 followed by two 200 mg tablets once a week for a total of 7 weeks.

Duration of treatment:

Study drug will be administered for 7 weeks.

Criteria for evaluation:

Efficacy: Rate of COVID-19 positive conversion on weekly nasopharyngeal (NP) sampling

Safety: Body temperature measurements, adverse events, and serious adverse events.

Statistical methods:

Sample size: A total sample of 360 individuals (180 in each arm) would provide at least 80% power to detect a relative risk reduction of 40% in the rate of positive NP samples when the anticipated rate of positive conversion among those taking hydroxychloroquine is approximately 30%.

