9.8.3. Inclusion/Exclusion

Inclusion and exclusion criteria must be reviewed as indicated in [Table 3](#). Subjects must meet all of the inclusion and none of the exclusion criteria for entry in the study. Investigators should contact the medical monitor with any questions regarding eligibility prior to enrolling the subjects on Day 1.

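### Committee reviews at about week 4 and then quarterly do not fit a 4-month study of a 7-week course: the second falls at about week 17, around or after the end of dosing

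*Protocol*

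**What the plan says.** Protocol section 9.4.1 sets the timetable in one sentence: the committee first looks at the data about 4 weeks after the first enrolment, and it "will continue to do so quarterly until the last dose of the last subject enrolled". The same section makes the committee responsible for following progress and accumulating data during the study, and lets it recommend continuation, modification for safety, or termination. It names no meeting triggered by enrolment or by events.

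The Synopsis fixes the length: "Studied period: 4 months Estimated date first subject enrolled: March 2020 Estimated date last subject completed: July 2020". It also states: "Study drug will be administered for 7 weeks". Section 7.1 says that "participants will be scheduled to be assessed in person at Days 7, 14, 21, 28, 35, 42 and 49". Table 3 marks drug administration from Day 1 to Day 42, with Day 49 as the end-of-study visit.

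Other safety oversight is described elsewhere in the Protocol. Section 11.7 requires serious adverse events to be reported within 24 hours and says they will be reviewed in aggregate regularly, without an interval or a named reviewing body. The SAP does not address committee reviews.

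**The concern.** A quarter is about 13 weeks, nearly twice the length of one subject's course. In a study that lasts only a little longer than a quarter, a quarterly rule yields few meetings, and their position decides whether the committee can do its job.

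The one review that clearly falls during dosing is at about week 4, when nobody can yet have completed a course. The next comes when dosing is ending or over, too late for a recommendation to protect more than a few subjects. What is lost is the committee's look at accumulating data from completed courses while others are still being treated. Non-serious adverse events are collected at every weekly visit, but the documents name no other aggregate review of them.

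**Working it through.** **Inputs**
- First review: about week 4 after first enrolment (Protocol 9.4.1).
- Later reviews: quarterly, up to the last dose of the last subject (9.4.1).
- First enrolment to last completion: 4 months, March to July 2020, both dates marked as estimates (Synopsis).
- Follow-up per subject: 7 weeks, to Day 49 (7.1). Last dose: Day 42, i.e. 6 weeks after the first (Table 3), or Day 49 if dosing runs the full 7 weeks. Both are carried through.
- Enrolment is taken as Day 1, in line with section 9.8.3 ("eligibility prior to enrolling the subjects on Day 1").
- Treated subjects: half of 360 = 180 (Synopsis).
- Accrual pattern: not given, so it is an assumption.

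**Study length.** 4 × 365.25 / 12 / 7 = 17.39 weeks. From 15 March to 15 July 2020 is 17.4 weeks, so the stated 4 months agrees with the stated dates.

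**Second review.** One quarter = 365.25 / 4 / 7 = 13.04 weeks. Second review = 4 + 13.04 = week 17.04.

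**End of dosing.** The last enrolment must be by 17.39 − 7 = week 10.39. The last dose is then at:
- Day 42 reading: 10.39 + 6 = week 16.4, before the second review.
- Day 49 reading: 10.39 + 7 = week 17.4, about 0.35 week after it.

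**Who has no committee review between first and last dose.** A subject enrolled at week *e* is missed if neither week 4 nor week 17.04 lies between *e* and the last dose.
- Day 42 reading: everyone with *e* > 4. Even accrual: (10.39 − 4) / 10.39 = 61.5%, or 0.615 × 180 ≈ 111.
- Day 49 reading: everyone with 4 < *e* < 17.04 − 7 = 10.04. Even accrual: (10.04 − 4) / 10.39 = 58.1%, or 0.581 × 180 ≈ 105.

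**Sensitivity.** Accrual shape is modelled as a cumulative share (*e* / 10.39)^k.

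| Change from the base case | Share missed |
|---|---|
| Front-loaded accrual, k = 0.5 (Day 42) | 1 − (4/10.39)^0.5 = 38% |
| k = 0.7 (Day 42) | 49% |
| Even accrual, k = 1 | 58% (Day 49) to 62% (Day 42) |
| k = 1.5 (Day 42) | 76% |
| Slow start, k = 2 (Day 42) | 1 − (4/10.39)^2 = 85% |
| Shortest March–July span, 13.1 weeks, even accrual | 34% |
| Longest March–July span, 21.7 weeks, even accrual | 41% (Day 49) to 48% (Day 42) |
| Quarter counted from first enrolment (week 13.04), even accrual, Day 42 | (7.04 − 4) / 10.39 = 29%, about 53 of 180 |

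These rows change one assumption at a time and span roughly 30% to 85%. Combining favourable assumptions goes lower: front-loaded accrual (k = 0.5) with the 13.1-week span gives 19%.

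**What needs no accrual assumption.** The earliest last dose is at week 6 (Day 42) or 7 (Day 49), so the week-4 review cannot include a completed course. At the stated 4 months, with the quarter counted from that review, the next review comes after dosing has ended or within days of its end.

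**The case against.** Four arguments have force.

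1. **Other oversight exists.** A reader might infer that no scheduled safety review of any kind happens in between. Section 11.7 rules that out: serious events are reported within 24 hours and reviewed in aggregate regularly, with expedited reporting of a signal. Section 7.4 lets the sponsor stop at any time. In a single-centre, open-label study, group-level events are also visible without a meeting. The gap is therefore in committee review only. It still stands, because the section 11.7 review has no interval and covers serious events.

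2. **The size rests on accrual.** A reader might infer that most treated subjects are missed. The documents give no accrual pattern, and several plausible readings put the share below half. At 4 months on the Day 42 reading, it is not a majority if half or more of the treated subjects enrol in the first 4 weeks.

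3. **The date of the second review depends on the reading.** It is tempting to say that only one review could ever change anything. If the quarter runs from first enrolment, the second review is at week 13, when the earliest subjects have finished and later ones may still be dosing. On the 21.7-week span, enrolment can run to about week 14.7, so a week-17 review also finds subjects on treatment. The first of these is the less natural reading of section 9.4.1, but the wording does not exclude it. Neither reading closes the gap: 29% and 41–48% remain under even accrual.

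4. **Individual protection is separate.** Section 5.1.6 notes QT prolongation, and Table 3 schedules no ECG or safety laboratory tests, so one might call committee review the main study-level safeguard. The documents do not bear that out. Section 8.2 excludes subjects with known QT risk, and section 9.4.1 has investigators decide on ECG and laboratory tests for each subject throughout.

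**Conclusion.** The mismatch holds. On the Protocol's own figures, the second committee review falls at about week 17 of a 17.4-week study, around or after the end of dosing, and may lapse because reviews stop at the last dose. At the stated 4 months this leaves essentially one usable committee review, held before anyone has completed a course.

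The share of treated subjects dosed entirely between reviews is about 60% under even accrual. That figure assumes a 4-month study, a quarter counted from the week-4 review, and enrolment on Day 1. The range is wide enough that the point should not be stated as a majority. It should also stay confined to the committee: expedited and aggregate review of serious events mitigates the gap, but does not give the committee the accumulating data it is charged with reviewing. The change is worth making because the interval does not fit the study length and is cheap to correct.

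**What to change.** In Protocol section 9.4.1, replace the quarterly interval with one shorter than the 7-week course. Every 4 weeks is one example: about weeks 4, 8 and 12, and again if dosing continues. At the stated 4 months this gives every treated subject at least one committee review during dosing: the interval of 4 weeks is shorter than the 6 weeks from first to last dose on the Day 42 reading, and the last subject, enrolled at about week 10.4, is still dosing at week 12. The week-8 review would also be the first able to include completed courses while others are on treatment.

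The same committee can do this with adverse event data already collected at the weekly visits. The cost is about two extra meetings and short data listings. No dose, visit, procedure or clinical rule changes.
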